Timeline. A 6 month startup is anticipated to put all procedures in place (e.g. hire/train part-time coordinators, obtain local committee approval, prepare mailed material for patients. 51 months will be devoted to recruitment of subjects and performance of scheduled unsedated colonoscopy using WE or WECAC. The last three months will be devoted to data analysis and preparation of reports.

Flow Chart Based on CONSORT Guideline

(d) Description of base population and groups to be studied.

Base Population. Patients without escorts or with a personal preference for no sedation will be given a standard description (Table 3) of the scheduled unsedated option by the research coordinator (15). Veterans who accept the option will receive standardized verbal and written description of the RCT. Those interested in participation will be given a description of the study and consent form will be mailed for review. Prior to the start of colonoscopy, any further questions will be addressed. The patients will be informed that the endoscopist will use maneuvers (e.g., loop reduction, removal of colonic luminal content, position change, abdominal compression) to minimize insertion pain. These will be recorded by the assistant. Topical lidocaine (2%) will be applied to the anal canal to minimize purge or hemorrhoid-related anal discomfort. All subjects will be informed that the colon will likely react to the presence of the colonsocope to "push it back out". This translates into a sensation of an urge to have a bowel movement. The reaction is normal and natural. More severe pain will be reported to the colonoscopist who will employ maneuvers to minimize the pain. During the examination if implemented maneuvers fail to keep pain at a tolerable level, insertion will be halted. Enrolled patients will sign informed consent before start of colonoscopy to agree to be randomized, to allow the colonoscopy examination be recorded for analysis, to respond to questionnaires before, immediately after and at 24 hours, weekly thereafter until 30 days after colonoscopy. Subjects who fail cecal intubation due to pain have the option to reschedule for a repeat colonoscopy under sedation (with usual escort requirement).

(e) Justification of endpoints, procedures and links between questions, data, and endpoints.

Primary outcome. Patient with insertion pain that cannot be brought to a tolerable level by colonoscopist implemented maneuvers will be considered failure of cecal intubation and the insertion will be discontinued. The pain level at the time of discontinuation will be noted for analysis.

Standardized validated instruments.

Proportion with no insertion pain, insertion time, proximal colon ADR (secondary outcomes in males) have been defined above; demographic data, co-morbidities, prior history and additional procedure based and patient level parameters will be analyzed as covariables (Tables 9 and 10).

Table 9: Demographic variables, co-morbidities and prior history				
Age	In years		Hemorrhoids	0=no, 1=yes
Gender	Male, female		Chronic pain treatments	0=no, 1=yes

Education	Elementary, high, college, graduate	Substance abuse	0=no, 1=yes
Ethnicity	White, Black, Hispanic, Asian, other	Prior abdominal surgery	0=no, 1=Yes (type)
BMI	Weight/height ²	Prior sedation colonoscopy	0=no, 1=yes
Indication	Screening, surveillance, diagnostic, pain	Prior unsedated colonoscopy	0=no, 1=yes

Table 10: Additional procedure based and patient level covariates				
Recalled maximum insertion pain	Maximum pain during insertion reported to a blinded observer after			
score (blinded data)	colonoscopy before discharge, VAS: 0=none, 10=most severe. Correlation with RTMIP.			
Overall ADR - entire colon	Proportion of patients with at least one adenoma of any size.			
Right colon ADR	ADR from cecum to hepatic flexure			
Adequacy of patient blinding	Patient guesses which method is used (<60% correct=adequate).			
Successful cecal intubation	0=no, 1=yes			
Successful cecal ilitubation	Abdominal pain prior to start of colonoscopy: 0, none to 3, severe (recorded			
Current abdominal discomfort	before examination)			
Loop reduction maneuvers	Number of times used, recorded by nurse assistant			
Position change	Start with left lateral, change as needed to supine, right lateral, prone.			
Abdominal compression	0=no, 1=Yes (sigmoid, transverse, hepatic, right side)			
Need to change technique	0=no, 1=yes (to air insufflation)			
Water volumes (insertion) Volume of water (infused and suctioned) upon arrival to the cecum, eq				
	volumes confirm appropriate application of water exchange			
Water volumes (total)	Volume of water (infused and suctioned) at the end of colonoscopy			
	Documented during withdrawal (4=excellent, no residual stool; 3=good, small			
Quality of bowel preparation	amount of residual stool; 2=fair, moderate amount of residual stool; 1=poor,			
	large amount of residual stool) (5)			
Failed (poor prep)	No. of patients in whom the cecum is not reached due to poor prep			
	Based on playback review of recorded procedure by blinded observer and			
Video data	tabulation of pertinent variables described above. Insertion and withdrawal			
	phase will be separately coded for blinded review			
Patient satisfaction	0=not satisfied, 10=very satisfied			
Willing to repeat same in future	0=not willing, 10=willing. Recorded by blinded observer prior to discharge.			
Recommend to family/friends	0=not willing, 10=willing. Recorded by blinded observer prior to discharge.			
Participant satisfaction	0=Not satisfied, 10=satisfied			
Reason for choice of unsedated	No ride, personal preference, other			
Abdominal discomfort today	0=none to 3=severe (recorded before examination)			
Expectation today	0=poor to 4=excellent (recorded before examination)			
Previous endoscopy experience	0=poor to 4=excellent (recorded before examination)			
Pain tolerance (patient reported)	0=poor to 4=excellent (recorded before examination)			
Subjective anxiety	0=none to 3=high (recorded before examination)			
Objective anxiety	0=none to 3=high (assessed by endoscopist before examination)			

Record keeping: A digital video recorder will be used to record the procedure to document procedure times (insertion, arrival in the cecal, biopsy, polypectomy, end of examination), cecal intubation (touching cecal floor) and the findings during the withdrawal phase. The digital images will bear no personal identifier.

Links. Enrolled patients will be randomized to 2 groups for examination. We can determine if WECAC will be superior to WE alone in providing low insertion pain. The influence of covariables on results of treatment can also be determined. The CONSORT guideline will be followed in reporting the data.

Standardization: During the start-up period, the PI will re-visit each site to facilitate standardization of WE and WECAC, and use of loop reduction, position change and abdominal compression maneuvers.

(f) Data collection methods, intervals, and follow-up procedures:

Prospective data gathering. Table 11 shows measures, their purposes, timing of data collection.

Table 11: Data to be monitored ^a	Baseline	During or after Colonoscopy	Up to 1 month follow up ^b
Co-variables: Demographic data interview & record review, detailed medical and surgical history, physical examination, e.g. anal rectal pain	Х		
Procedural data, primary outcome: RTMIP (unblinded); patient guesses which method has been used, recalled maximum insertion pain score (blinded) [validates primary] c		Х	
AE, adverse events; SAE, serious adverse events.		Х	X

^aData obtained by investigators, nurse assistants or coordinators at visits; ^bData obtained by mailed questionnaires and follow up telephone calls; ^cQuestionnaires will be completed not in the presence of the therapist(s).

Training and quality control measures to assure accuracy, precision and validity of the data Throughout the 6-month start-up period, training of study personnel will take place by way of conference calls by all participating investigators, site research coordinators and statistic core personnel. Case report forms will be finalized and a detailed manual of study operations will be written and circulated. This manual will serve as the training manual for the meetings and as a reference document following the meetings. The PI's office and the data coordinating team will provide the training.

The general training will include the study treatment, patient screening and consent, baseline evaluation, follow-up procedures, and proper entry and maintenance of data (assisted by statistics core personnel). Research coordinators from all participating sites will be trained in the administration of a variety of state-of-the-art assessment instruments to insure accuracy and precision of administration of the instruments to maximize inter-rater reliability.

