Exclusion criteria. Decline to be randomized, unable to give consent or respond to questionnaires, history of colon surgery, active inflammatory bowel disease, lower gastrointestinal bleeding (except for occult blood or FIT positive in the context of colon cancer screening), therapeutic colonoscopy (e.g., hemostasis, removal of large polyp), proctosigmoidoscopy, bidirectional endoscopy, inadequate consumption of bowel preparation, known history of severe diverticulosis or diverticulitis, history of abdominal surgery previously requiring sedation for colonoscopy, current narcotic/anxiolytic medication use, prior unsuccessful experience with unsedated colonoscopy, emergent colonoscopy, evidence of colonic obstruction based on pre-colonoscopy clinical evaluation, current participation in other studies, medical condition that could increase the risk associated with colonoscopy (e.g., active cardiac or pulmonary disease or other serious disease), medical condition that would preclude a benefit from colonoscopic screening (e.g., cancer or any terminal illness), prosthetic heart valve, anticoagulant therapy, nonmedical problems (e.g., psychiatric disorders, excessive use of alcohol), need for special precautions in performing colonoscopy (e.g. antibiotic prophylaxis), and request of on demand sedation.

Primary outcome measure (for male and female subjects).

	_
Real time maximum insertion	_
pain (RTMIP) (unblinded) score	
(validation by correlation with	
recalled pain described below)	

Pain during insertion reported to the unblinded assisting nurse, visual analogue scale, VAS: 0=none, 10=most severe. The highest pain score will be tabulated for analysis. Timing of data collection will be at the discretion of the nurse to minimize bias by colonoscopist behavior.

Secondary outcome measures (for male and female subjects).

Proportion with no insertion pain Proportion report no pain during insertion of the colonoscope. Quality marker.

Insertion time	Time to cecum (clock display on monitor). Faster insertion is a quality marker
Proximal colon ADR	ADR from cecum to splenic flexure. Measure of high quality colonoscopy

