Study technique (WECAC) (Table 8). (11,12,47) A FDA approved, commercially available transparent cap (Olympus) will be fitted to the colonoscope tip. The usual and adjunct maneuvers otherwise are similar to those of WE described above. Sporadic reports suggested the cap reduced insertion pain when air was used (58-61). The effect of the cap plus WE on pain has not been reported in RCT. The pilot (11) and preliminary data (12,47) of the current team do indicate WECAC reduces RTMIP compared to historical cohorts. The possible mechanism of further reduction of insertion pain is not known. The cap may ease the pinpointing of the correct location of the collapsed lumen (22) by maintaining separation of the mucosa from the lens of the colonoscope, improving visualization in a non-distended colon. The cap is particularly helpful at acute bends in the air filled lumen (62-65).

Table 8: Content of colonoscopy insertion techniques	WE	WECAC
Cap attached to tip of colonoscope		/
Split-dose bowel preparation, begin without medication, air pump off before start of examination, small towel cover eyes during insertion for blinding patient to the technique used, air pocket and residual feces suctioned during insertion, infused water suctioned predominantly during insertion, frequent loop reduction, change position if scope tip does not advance despite loop reduction, abdominal compression if scope tip does not advance despite above maneuvers	1	1

Patient and procedure factors affect insertion pain. Proper randomization will distribute these factors evenly amongst the groups. Change in the subject pool over time may occur as the trial may extend over years. The types of patients attending the clinic may change. Block randomization ensure that comparable numbers of subjects are assigned to each arm at each period of the study.

Standard tools will be used to ensure as far as possible that all patients are prepared and examined similarly, with only the dependent variables varying systematically between groups.

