Updated male Veteran sample size. Pilot data in scheduled unsedated male Veterans were updated. The real time maximum insertion pain (RTMIP) [mean (SD)] was 2.7 (2.2) with WE (n=87) and 1.5 (2.1) with WECAC (n=38). The reduction (44%) 2.7-1.5=1.2 is 1.2/2.2=0.55 standard deviation (SD) units. The sample size/group needed to detect a difference at a level of significance of 0.0492 (adjusted for Obrien-Fleming interim stopping rules, one interim analysis at 50% completion) with 90% power is 72 or 144 total using a twosided two sample t-test. Assuming 90% of subjects will be evaluable, we plan to recruit 160 male Veterans. Updated pilot data showed the PI performed 30 scheduled unsedated colonoscopies (male) in 1 year when ~2200 colonoscopies were offered at VAGLAHS (1.36%). At participating sites, a total of ~9000 colonoscopies (VAGLAHS 2200, VANCHCS 3300, VAPAHCS 3500) will be performed each year. For purpose of conservative estimation, 1/2 of 1.36% (0.68%) of all colonoscopies will be presumed to be in scheduled unsedated male Veterans when the option is made available up front. In 51 month (4.25 year) enrollment period, a total of 38250 colonoscopies will be performed. 260 (0.68% of 38250) male Veterans will receive scheduled unsedated colonoscopy, making target enrollment of 160 achievable (only 160/260 = 62% enrollment rate needed). In support of this possibility, in two prior RCT in scheduled unsedated male Veterans at VAGLAHS and VANCHCS comparing WE vs. air colonoscopy, high enrollment rates of 97.7% (84/86) and 95.2% (100/105), respectively, were recorded. Sample size of 160 will be sufficient to show significant differences in some of the previously listed secondary outcomes related to quality colonoscopy in

Secondary outcome power estimates based pilot data in WE (n=87) and WECAC (n=38) in male Veterans					
Secondary Outcomes	Pilot (WE vs. WECAC)	Difference (SDU or %)	Sample size per group needed*		
Recalled pain, score (SD)	1.5(2) vs. 0.5(2)	1 (0.5 SDU)	84 (Will be dropped)		
Successful cecal Intubation	98% vs. 100%	2%	(Will be dropped)		
Proportion with no pain	18% vs. 46%	28%	54		
Insertion time, minutes (SD)	15(5) vs. 12( 5)	-3 (0.6 SDU)	58		
Overall ADR - entire colon	36% vs. 50%	14%	258		
Proximal colon ADR	17% vs. 40%	23%	76		
Right colon ADR	20% vs. 40%	20%	106		
Willing to repeat, score (SD)	9.0(2.5) vs. 9.6(0.9)	0.6 (0.4 SDU)	(Will be dropped)		

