In both male and female Veterans, record will be kept of all these variables, however, to demonstrate comparability of the study and control groups. When the male and female data are combined, the sample size may reveal differences between WE and WECAC that are worth pursuing, thus providing pilot data for future studies (e.g. overall and segmental adenoma detection rates in scheduled unsedated subjects).

Statistical Analysis. Analysis will be performed based on assigned groups using STATA software (StataCorp 2013. Stata Statistical Software. College Station, TX: StataCorp LP). Descriptive statistics (frequencies, measures of central tendency and dispersion) will be used to evaluate the distribution of each variable. Data as mean (SD) or median (IQR) will be assessed by 2-samples independent samples tests (e.g. Student's t), Fisher exact test; relative risk tests and correlation analysis will be used to evaluate hypotheses. P<0.05 will be considered significant. Statistical assumptions required will be checked and appropriate data transformations or non-parametric test (e.g. Wilcoxon-Mann-Whitney *U test*,) will be used if assumptions are not met. Linear regression will be used to determine significant factor(s) that impact on the primary outcome. The analysis will use intention-to-treat principles, i.e., all randomized patients will be included in the analysis even if their colonoscopies were discontinued early (e.g., pain, poor preparation). The pain score at discontinuation will be used for the analysis for patients with early discontinuation.

Hypotheses Testing. There will be one-interim analysis and a final analysis for this study. The interim analysis will be conducted after 50% of subjects have been evaluated. This interim analysis will be for the primary analysis alone. The significance level for the interim analysis will be 0.0054 based on the standard O'Brien-Flemming rule. The study will be stopped if there is a significant result for the interim analysis. The final analysis will use a 0.0492 level of significance.

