- 2. Changes from sedated to unsedated and air to WE require deviation from the norm, and carry a high risk that the study results would not lead to a change in future practice. The PI has shown that when scheduled unsedated colonoscopy was introduced, 76% (increase from 36%) of colleagues at the West LA VAMC are willing to perform unsedated colonoscopy, and nearly half have taken up use of WE (15). We anticipate demonstration of a less painful technique will improve acceptance of the novel approaches.
- 3. The cap adds an extra cost. The proposed RCT will seek data to indicate the added cost is justifiable, if WECAC is indeed less painful than WE in the unsedated Veterans.
- 4. The study should include strict control groups of air or CO2 to aid insertion. We have shown that WE produces significantly less insertion pain than air or CO2 insufflation during insertion (4). The use air or CO2 to aid insertion in control groups cannot be justified in the unsedated Veterans in the current protocol.
- 5. Local VAMC provided transportation will obviate the need to provide scheduled unsedated colonoscopy. The approach is not appropriate for Veterans with a preference for no sedation.
- 6. Development of enhanced service to Veterans is more appropriately grouped under health service research. The proposal does focus on techniques directly implemented by the colonoscopist and is therefore a clinical endoscopic service. Clinical research funding is therefore appropriate.
- 7. The colonoscopist and nurse cannot be blinded to treatment allocation and the primary outcome of RTMIP. The measure has been repeatedly validated (4,5,32). Randomly selected (determined by the statistician) coded digital records will be reviewed by an independent observer to confirm agreement of findings, success of cecal intubation, time taken (endoscopic clock) for insertion to the cecum. Other types of self-selection bias are more difficult to control by blinding. The ongoing results will not be disclosed to the endoscopists, who may change the approach if it is known that one group is doing better or worse than the other. All investigators will be blinded to study results until completion of data collection.

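### The primary endpoint is the highest of pain scores taken when an unblinded nurse chooses to ask, so unequal asking between arms would shift it; script and count the readings.

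*Protocol*

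**What the plan says.** The primary outcome table in the protocol (section (4) Work Proposed, (b)) defines RTMIP in three steps.

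- The source and scale: "Pain during insertion reported to the unblinded assisting nurse, visual analogue scale, VAS: 0=none, 10=most severe".
- The summary: "The highest pain score will be tabulated for analysis".
- The schedule: "Timing of data collection will be at the discretion of the nurse to minimize bias by colonoscopist behavior".

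The SAP section on potential problems (item 7) accepts that "The colonoscopist and nurse cannot be blinded to treatment allocation and the primary outcome of RTMIP". It relies on earlier validation of the measure and on independent review of coded video. That review covers findings, cecal intubation and insertion time, not pain scores.

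The abbreviated protocol (Colonoscopy Procedure, item 8) says only that pain scores are monitored and recorded. Tables 9 to 11 do not list the number of readings, and the primary test in the SAP does not use it. Recalled maximum pain, given to a blinded observer before discharge, is collected (Table 10) to be correlated with RTMIP. It is dropped as a secondary outcome in both sexes, but the SAP keeps a record of it.

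Table 8 lists, for both arms, "small towel cover eyes during insertion for blinding patient to the technique used".

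**The concern.** Giving the timing to the nurse limits what the colonoscopist can do, but it moves the same freedom to a second person who knows the arm. Because no number of readings is set, freedom over timing is also freedom over frequency.

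The expected maximum of several readings cannot fall when a reading is added, and it rises whenever pain varies within a patient. A nurse who asks more often in one arm raises that arm's RTMIP with every score recorded honestly. More asking in the WE arm would create or enlarge an apparent benefit of the cap. More asking in the WECAC arm would hide a real one. The secondary outcome of no insertion pain is exposed in the same way, because each extra question is another chance of a score above the threshold.

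Patient blinding does not help, since the patient does not choose when to be asked. Correlation with recalled pain does not help either: adding a constant to RTMIP in one arm leaves the correlation within each arm unchanged.

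**Working it through.** **1. The plan's own figure.** The SAP gives the male pilot values as "The real time maximum insertion pain (RTMIP) [mean (SD)] was 2.7 (2.2) with WE (n=87) and 1.5 (2.1) with WECAC (n=38", and "The reduction (44%) 2.7-1.5=1.2 is 1.2/2.2=0.55 standard deviation (SD) units". At the final level of 0.0492 ("The final analysis will use a 0.0492 level of significance") with 90% power:

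n per group = 2 × (1.967 + 1.282)² / (1.2/2.2)² ≈ 71 by the normal approximation, and 71.9, so 72, by the exact t calculation.

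The stated 72 per group reproduces (power 0.900), as does 144/0.9 = 160 recruited. The planned effect of 1.2 points is the yardstick below.

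**2. Effect of the number of readings, with identical pain in both arms.** The documents give neither the number of readings nor the within-patient variation. Both are assumptions here.

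- One reading = patient mean + between-patient deviation (SD 1.8, assumed) + within-patient deviation (SD w, assumed 1.0 or 2.0), bounded to 0–10 and rounded.
- RTMIP = highest of k readings.
- The overall mean is set so that k = 4 gives 2.7, the male WE pilot mean. The simulated SD at k = 4 is 1.8 (w = 1.0) or 2.1 (w = 2.0), against 2.2 in the pilot.
- 400,000 simulated patients per setting.

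| w | Mean RTMIP, k = 4 | Mean RTMIP, k = 5 | Shift | Share of 1.2 | Score of zero, k = 4 → 5 |
|---|---|---|---|---|---|
| 1.0 | 2.70 | 2.82 | 0.12 | 10% | 13.5% → 12.0% |
| 2.0 | 2.70 | 2.93 | 0.23 | 19% | 18.4% → 14.8% |

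Five against four is one question every 3 minutes (assumed) over the male pilot insertion times of 15 and 12 minutes in the SAP: 15/3 = 5 and 12/3 = 4.

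The Significance section of the protocol treats a score below 2 as no pain. On that threshold the share moves by about 2.4 (w = 1.0) to 4.5 (w = 2.0) percentage points.

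**3. Consequence for the primary test (72 per group, SD 2.2, two-sided 0.0492).**

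| Shift | False-positive rate if there is no true effect | Power for a true 1.2 if the extra readings fall in WECAC |
|---|---|---|
| 0 | 4.9% | 90% |
| 0.12 | 6.1% | 83% (net 1.08) |
| 0.23 | 9.4% | 75% (net 0.97) |

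**4. A second model.** This one is calibrated to both the pilot mean and SD at four readings, with within-patient correlation assumed from 0.9 down to 0.3. Five against four then gives 0.09 to 0.29 points and a false-positive rate of 6% to 13%. The order of size is the same.

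**5. Volunteered pain.** If a share v of patients report their peak unprompted, and RTMIP in those patients no longer depends on the number of prompts, the shift is multiplied by (1 − v). With v = 0.8 (assumed): 0.2 × 0.12 = 0.024 and 0.2 × 0.23 = 0.046 points.

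**The case against.** The strongest reply is that nothing shows nurses will ask unequally, and that patients are awake. The Base Population section of the protocol says that more severe pain will be made known to the colonoscopist, who responds to it. If peaks are usually volunteered, the number of prompts matters little. This stands: it limits the size, but does not remove the exposure.

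A reader might go further than the documents allow in four ways.

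- **That the bias favours WECAC because its insertion is shorter.** The male pilot has 12 against 15 minutes, but Table 6 has WECAC at 20 and 18 minutes and WE at 34 and 13. The direction is not settled. A lower maximum from a truly shorter insertion, with even-handed asking, is also arguably part of the technique's effect.
- **That the shift could approach half of the planned effect.** Five readings against three would give 0.28 to 0.52 points (23% to 43% of 1.2), but no figure in the documents supports that contrast.
- **That the damage could not be examined afterwards.** Pain scores are recorded, in the plural. Blinded recalled pain is kept and does not depend on the number of prompts. In the non-randomised male pilot it differed by 1.5 − 0.5 = 1.0 point, against 1.2 for RTMIP, which does not suggest that reading counts drive the gap. The case report forms and operations manual were still to be finalised and might hold a schedule, which would then need reconciling with the protocol.
- **That the visual scale forces the towel to be lifted.** The protocol has pain reported to the nurse and the eyes kept covered, so a spoken number is the natural reading. This is a matter of naming.

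**Conclusion.** The concern holds as a conditional weakness. The endpoint is a maximum, the number of readings is open and is not a listed variable, and the person who decides on it knows the arm. That a maximum rises with the number of readings is a mathematical property and needs no assumption beyond pain that varies during insertion.

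Whether counts will differ, in which direction, and by how much is unknown. The illustrative 0.12 to 0.23 points rests on one extra reading in one arm, within-patient SDs of 1.0 to 2.0, a between-patient SD of 1.8, and no volunteered peaks. A shift of that size would not by itself account for a 1.2-point difference. It could raise the male false-positive rate from about 5% to between 6% and 9%, or take a real effect below the planned power. The change is worth making because it costs little and protects the only primary endpoint, not because bias has been shown.

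**What to change.** - **Script the prompts.** Replace nurse discretion with a fixed script, the same in both arms. The nurse asks for a spoken 0–10 score at set points of insertion that the nurse can identify without a cue from the colonoscopist (for example from the monitor), and at the point of halting if insertion stops early. Any spontaneous report is added. RTMIP is the highest of these. Points along the colon, rather than clock intervals, keep the count from depending on insertion time.
- **Record and report.** Enter every score and the number of scores on the case report form, and report the count by arm.
- **Add a sensitivity analysis.** Compare blinded recalled maximum pain between arms, alongside the planned correlation. The data are already to be collected.
- **Name the scale.** Call it a verbal 0–10 rating, which fits the covered eyes, and state which score counts as no pain.

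Cost: protocol, SAP and case report form wording, a few more questions per insertion, and an item in the start-up training already planned. The nurse and the procedure stay the same. The prompt points must be chosen with care, because prompts that need the colonoscopist to announce position would hand the timing back to the person whom the present rule was meant to exclude.
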